3.1.6. Group C Phase 2 (Dose Expansion): Entospletinib Monotherapy

Note: At the time of this amendment, Cohort C1A had completed enrollment (n=15). This amendment identifies the closure of Cohort C3 to further enrollment (n=12).

Relapsed/refractory and previously untreated subjects will be evaluated in separate cohorts during phase 2 as monotherapy. ENTO 400 mg will be administered orally every 12 hours on Days 1-28 of every 28-day cycle as long as the subject is experiencing benefit and does not meet criteria for study treatment discontinuation.

A bone marrow biopsy and aspirate sample will be collected for disease assessment and biomarker research at the end of Cycles 1 and 2 on Day 28. A bone marrow aspirate sample will also be collected for disease assessment and biomarker research on Day 28 of every 4 cycles beginning on Cycle 4 Day 28 (eg, Cycle 4 Day 28, Cycle 8 Day 28) and at suspected disease progression. Subjects who achieve CR/CRi that is stable for 2 consecutive bone marrow evaluations are not required to have further bone marrow aspirate samples collected, unless clinically indicated.

Cohort C1A: This cohort is designed to enroll 15 relapsed/refractory AML subjects. If 5 or more of the initial 15 subjects achieve CR/CRi after 1-2 cycles, an additional 15 subjects would then be enrolled. However, if less than 5 of the initial 15 subjects achieve CR/CRi after 1-2 cycles, then treatment would be considered futile. At this time, futility has been met and, thus, Cohort C1A will not move forward (ie, will not enroll any subjects).

Cohort C2: 15 relapsed/refractory AML subjects with MLL.

Cohort C3: 30 previously untreated AML subjects who are unfit (eg, very elderly, have multiple comorbidities, and a poor ECOG/performance status) for chemotherapy or hypomethylating agent, or refuse either of these 2 treatment options.

If a subject discontinues study treatment (eg, as a result of an AE), every attempt should be made to keep the subject in the study to perform the required study-related follow-up and procedures. If this is not possible or acceptable to the subject or investigator, the subject may be withdrawn from the study.

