6.3. Treatment Assessments

Subjects who have met all eligibility criteria will come to the clinic on Cycle 0 Day 1 (Cycle 1 Day 1 for Group C) to perform study required procedures prior to dosing, review prior/concomitant medications, and record adverse events at each clinic visit.

For study purposes, the ENTO lead-in (Cycle 0) is 14 days for Groups A, B, and C. One cycle of induction therapy is 14 days (or up to 28 days depending on count recovery) for Group A, and 28 days for Groups B and C.

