8.1.2. Endpoints

Primary Endpoints:

Safety

- Occurrence of adverse events and laboratory abnormalities defined as DLTs for ENTO in combination with standard dose cytarabine and daunorubicin (7+3) in subjects with previously untreated AML (Group A)
- Occurrence of adverse events and laboratory abnormalities defined as DLTs for ENTO in combination with decitabine or azacitidine in subjects with previously untreated AML who are unable to receive 7+3 chemotherapy (Group B)

- Occurrence of adverse events and laboratory abnormalities defined as DLTs for ENTO as a single agent in subjects with relapsed/refractory AML with or without MLL or previously untreated AML (Group C)

Efficacy

- Complete remission rate at induction completion: defined as the proportion of subjects who achieved morphologic complete remission (CR) at induction completion. Note: CR includes a subcategory of cytogenetic CR (CRc).
- Composite complete remission rate at induction completion: defined as the proportion of subjects who achieved CR or morphologic complete remission with incomplete blood count recovery (CRi) at induction completion.
- Overall response rate at induction completion: defined as the proportion of subjects who achieved CR, CRi, or partial remission (PR) at induction completion.

Secondary Endpoints:

Exposure

- Drug administration and duration of exposure of study treatment

Safety

- Occurrence of AEs and laboratory abnormalities not defined as DLTs

Efficacy

- Event free survival (EFS) – defined for all subjects and it is measured from the start of the study therapy until the date of treatment failure, AML relapse or death from any cause, whichever occurs first
- Overall survival (OS) – defined as the interval from the start of the study therapy to death from any cause

Exploratory Endpoints:

CCI

- █ [REDACTED]
- █ [REDACTED]
- █ [REDACTED]
- █ [REDACTED]

[REDACTED]

[REDACTED]

[REDACTED]

[REDACTED]

[REDACTED]

[REDACTED]

[REDACTED]

[REDACTED]

[REDACTED]

[REDACTED]

[REDACTED]

[REDACTED]

[REDACTED]

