6.1. Primary Efficacy Endpoints

6.1.1. Definition of the Primary Efficacy Endpoints

- Complete remission rate at induction completion: defined as the proportion of subjects who achieved morphologic complete remission (CR) at induction completion. Note that CR includes a subcategory of cytogenetic CR (CRc)
- Composite complete remission rate at induction completion: defined as the proportion of subjects who achieved morphologic complete remission (CR) or morphologic complete remission with incomplete blood count recovery (CRi) at induction completion
- Overall response rate at induction completion: defined as the proportion of subjects who achieved morphologic complete remission (CR), morphologic complete remission with incomplete blood count recovery (CRi), or partial remission (PR) at induction completion

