6.1.2. Analysis of the Primary Efficacy Endpoints

Complete remission rate, composite complete remission (CR/CRi) rate, and overall response (CR/CRi/PR) rate at induction completion for Groups A and B will be summarized and the corresponding 95% exact CIs based on Clopper-Pearson method will be presented.

Response at induction completion is defined as the best response across the time points that occurred after day 1 of last cycle of induction therapy, and prior to the earliest of cycle 1 day 1 of post-remission or maintenance therapy, date of SCT and date of other anticancer therapy (excluding SCT and conditioning regimen (listed in Appendix 2)). Best response is the best outcome according to the ranking below by decreasing favorable level:

- 1) Cytogenetic Complete Remission [CRc]
- 2) Morphologic Complete Remission [CR]
- 3) Morphologic Complete Remission with Incomplete Blood Count Recovery [CRi]

- 4) Partial Remission [PR]
- 5) Morphologic Leukemia-free State [MLFS]
- 6) Relapse
- 7) Other

The category “Other” includes 3 subcategories: Treatment Failure [TF], Early Treatment Assessment [ETA], and No Assessment Done. For subjects who had response assessment in the last cycle but didn’t achieve any of the first 6 categories listed above at induction completion, TF will be the response at induction completion for those who received 2 induction cycles in Group A or received ≥ 2 induction cycles in Group B, and ETA will be the response at induction completion for those who only received ≤ 1 induction cycle. All subjects in “Other” will be considered as nonresponders and will be included in the denominator when calculating the remission rates at induction completion.

Complete remission rate, composite complete remission (CR/CRi) rate, and overall response (CR/CRi/PR) rate per best overall response ever achieved during the treatment for Group C will be summarized and the corresponding 95% exact CIs based on Clopper-Pearson method will be presented.

Best overall response is defined as the best response across all time points prior to SCT and other anticancer therapy (excluding SCT and conditioning regimen). Best response is the best outcome according to the ranking below by decreasing favorable level:

- 1) Cytogenetic Complete Remission [CRc]
- 2) Morphologic Complete Remission [CR]
- 3) Morphologic Complete Remission with Incomplete Blood Count Recovery [CRi]
- 4) Partial Remission [PR]
- 5) Morphologic Leukemia-free State [MLFS]
- 6) Other

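### SAP 6.1.2 uses best overall response for Group C in place of the induction-completion endpoint without listing the change, so the pooled relapsed/refractory futility table does not match the 1-2-cycle rule it serves

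*SAP*

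**What the plan says.** **Endpoint definition.** Protocol 8.1.2 gives the composite endpoint as "Composite complete remission rate at induction completion: defined as the proportion of subjects who achieved CR or morphologic complete remission with incomplete blood count recovery". It has no separate version for Group C. SAP 6.1.1 repeats it ("Composite complete remission rate at induction completion: defined as the proportion of subjects who achieved morphologic complete remission (CR) or" CRi), again for all groups.

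**Group C induction.** Protocol 6.3 gives the length of an induction cycle as "28 days for Groups B and C", but not how many such cycles make up induction in Group C. Protocol 3.1.6 and 3.4 let Group C treatment run on while the subject benefits.

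**Group C analysis.** SAP 6.1.2 applies the induction-completion definition to Groups A and B only. What it summarizes instead is the "rate per best overall response ever achieved during the treatment for Group C". The window has no cycle limit: "Best overall response is defined as the best response across all time points prior to SCT and other anticancer therapy". For Groups A and B the same measure is a sensitivity analysis. SAP 6.5, which lists departures from the protocol's efficacy analyses, mentions only time to blast clearance and MRD.

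**Futility rule.** Protocol 3.1.6 states for Cohort C1A: "If 5 or more of the initial 15 subjects achieve CR/CRi after 1-2 cycles", a further 15 are enrolled; with fewer than 5, treatment is judged futile. SAP 1.2 keeps the same rule and forms the 15 from nine eligible Phase 1b subjects and six C1A subjects. Protocol 8.9 and SAP 1.3 give an 84% chance of stopping at a true rate of 20%, and 22% at 40%. Both documents report that futility has been met.

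**Pooled analysis (1).** SAP 3.2 says this pooling of Phase 1b relapsed/refractory subjects with C1A is for futility. The introduction to SAP Section 6 sends the pooled Group C sets through Sections 6.1 to 6.3.

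**The concern.** Two definitions meet in one table. The futility rule counts responses after 1-2 cycles. The table presented as the futility analysis counts responses at any time before transplant or other anticancer therapy. A reader of the study report would naturally set that count against 5 of 15 and against the 84% and 22%, none of which was worked out for a best-ever count.

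Behind this lies a gap in the endpoint itself. Induction completion has no stated meaning for Group C, and the SAP resolves it with the widest window available. That may be a reasonable choice for continuous monotherapy. But it replaces the stated definition of a primary endpoint, and the section meant to disclose such changes does not mention it.

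**Working it through.** **1. Reproduce the plan's figures.** Inputs (Protocol 8.9, SAP 1.3): n = 15; stop if X ≤ 4; true rates 20% and 40%.

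P(stop) = Σ (k = 0 to 4) C(15,k) p^k (1−p)^(15−k)

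- p = 0.20: 0.0352 + 0.1319 + 0.2309 + 0.2501 + 0.1876 = 0.836, against the stated 84%.
- p = 0.40: 0.217, against the stated 22%.

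Both reproduce. They hold for one response definition with rate p, which in the rule is CR/CRi after 1-2 cycles.

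**2. Compare the two counts in the same 15 subjects.** Let E be the number with CR/CRi after 1-2 cycles and B the number with CR/CRi as best overall response, both using assessments before transplant or other anticancer therapy. Anyone in E is also in B, so B ≥ E. B exceeds E only if someone first reaches CR/CRi later. That is possible because Protocol 3.1.6 schedules marrows on Day 28 of Cycles 1 and 2, then at Cycle 4, Cycle 8 and so on, and at suspected progression.

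It follows that B below 5 implies E below 5. If B is 5 or more, the table alone cannot show whether the rule's count was met.

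**3. Size, for illustration only.** The documents give no late-response rate, so the increments below are assumptions. Keep the 1-2-cycle rate at 20% and apply the formula in step 1 to the best-ever rate.

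| Assumption about late response | Best-ever rate | P(fewer than 5 of 15) |
|---|---|---|
| None | 20% | 0.836 |
| 5% of early non-responders convert: 0.20 + 0.80 × 0.05 | 24% | 0.719 |
| 5 points added | 25% | 0.686 |
| 10% of early non-responders convert: 0.20 + 0.80 × 0.10 | 28% | 0.585 |
| 10 points added | 30% | 0.515 |

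At a 1-2-cycle rate of 40%, conversion of 5% or 10% of early non-responders gives best-ever rates of 43% or 46% and moves 0.217 to 0.155 or 0.106.

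**4. Check disclosure.** The endpoint in SAP 6.1.1 and the Group C analysis in SAP 6.1.2 differ, and SAP 6.5 does not list the difference. SAP 6.1.2 itself shows that the measures can disagree: its worked example for Group A is a partial remission by best overall response and a relapse at induction completion.

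**The case against.** The strongest reply is that Group C has no induction phase to complete. Protocol 6.3 is weak evidence of one: the same paragraph also assigns Group C a 14-day lead-in, although Group C starts at Cycle 1. On this view, best overall response is the natural measure for continuous monotherapy, and SAP 6.1.2 states it openly. This stands as a reason for the choice. It does not explain why SAP 6.1.1 and 6.5 are silent.

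The contrast with Groups A and B is also less sharp than it looks, because their induction-completion response is itself a best response, taken over a window starting in the last induction cycle. True, but that window is bounded.

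Late responses may be few. SAP Section 1 records a lack of responses to monotherapy, and Protocol 6.4.1, under the Group C blast-increase criteria, restricts continuation past Cycle 2 without signs of benefit. All analyses are descriptive, and the response, time-to-remission and marrow listings would let a reader rebuild early response. These points limit the consequence. They do not supply a table that applies the stated rule.

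A reader might go further and infer that the protocol fixes Group C's primary endpoint at 1-2 cycles. It does not: that time point belongs only to the C1A futility rule, not to C2, C3 or the pooled untreated set.

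**Conclusion.** The point holds as a mismatch between definition and analysis, with an omission in SAP 6.5. Group C's primary rates are analysed on a measure that neither Protocol 8.1.2 nor SAP 6.1.1 states, and pooled analysis (1) is labelled for futility but does not apply the futility criterion.

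It would be tempting to conclude that the 84% and 22% are wrong, or that the stopping decision is in doubt. The documents support neither. Both figures reproduce, the rule is worded at 1-2 cycles in both documents, and it has already been applied; a later summary cannot change it. Nor do the documents show that the Group C rates are inflated by any particular amount. The direction follows from the definitions, since best-ever cannot be lower. The size depends on a late-response rate that is not given, so 69% and 52% only illustrate what happens if the best-ever rate were 25% or 30%. With no late responders the shift is zero.

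The practical effect on conclusions is probably small. The correction is still worth making, because it concerns a primary endpoint and a table that could be misread.

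**What to change.** - **Pooled analysis (1):** report the CR/CRi count after 1-2 cycles (by Cycle 2 Day 28) as the futility result, beside the 5-of-15 boundary. Show best overall response separately and state that the boundary does not apply to it.
- **Other Group C cohorts and the pooled untreated set:** add CR, CR/CRi and CR/CRi/PR by the end of Cycle 2 alongside best overall response, each clearly labelled. The documents give no basis for demoting best overall response here, and doing so would hide genuine later remissions.
- **SAP 6.5:** record that Group C uses best overall response in place of response at induction completion, because the end of induction is not defined for open-ended monotherapy. Add a matching note in SAP 6.1.1.

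The cost is about one extra table per cohort and a few lines of SAP text. The Cycle 1 and Cycle 2 Day 28 marrows are already scheduled, so no new data are needed and treatment does not change.

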6.2. Secondary Efficacy Endpoints

6.2.1. Definition of Secondary Efficacy Endpoints

- Event free survival (EFS) - defined for all subjects and it is measured from the start of the study therapy until the date of treatment failure, AML relapse or death from any cause, whichever occurs first
- Overall survival (OS) – defined as the interval from the start of the study therapy to the death from any cause

Every attempt will be made to ensure that complete death dates are recorded. In those rare instances where complete death dates are not recorded, the following algorithm will be used:

- If day is missing but the month and year are available, then the imputed day will be the first day of the month or the last known alive date + 1, whichever is later.
- If day and month are missing but year is available, then the imputed date will be 01Jan of that year or the last known alive date + 1, whichever is later.

6.2.2. Analysis of the Secondary Endpoints

Subjects will be considered as treatment failure if having at least one efficacy assessment prior to SCT and other anticancer therapy (excluding SCT and conditioning regimen) but none of these efficacy assessments is CRc, CR, CRi, or PR; date of treatment failure will be the date of last adequate efficacy assessment prior to SCT and other anticancer therapy (excluding SCT and conditioning regimen). The events and censoring rules are detailed in [Table 6-1](#). Of note, other anti-cancer therapy excludes SCT and conditioning regimen in this table, and the criteria are hierarchical: subjects who meet the criteria on the top will be excluded from the criteria on the bottom.

Table 6-1. Event/Censoring Rules for EFS

Criteria	Event or Censored	Date of Event/Censoring
Relapse, no other anti-cancer therapy or prior to the start of other anti-cancer therapy, and 
 • had SCT prior to relapse, OR • no SCT prior to relapse, and days from last response assessment prior to relapse to relapse was within the following window (2 consecutive response assessments): For Group A: — ≤60 days (2 cycles (including the time waiting for	Event	Date of first relapse

count recovery) + 4 days) if didn't receive post-remission cycle
 
— <=120 days (4 cycles + 8 days) if received post-remission cycle but didn't receive ENTO mono maintenance cycle
 
— <=240 days (8 cycles + 16 days) if received ENTO mono maintenance cycle
		

For Group B:
 
— <=120 days (4 cycles + 8 days) if didn't receive maintenance cycle
 
— <= 240 days (8 cycles + 16 days) if received maintenance cycle
 
For Group C:
 
— <= 60 days (2 cycles + 4 days) if received <= 2 cycles
 
— <= 120 days (4cycles + 8 days) if received 3-4 cycles
 
— <= 240 days (8 cycles + 16 days) if received > 4 cycles
		

Treatment failure, and days from last response assessment prior to treatment failure or first dosing date, whichever is later, to treatment failure was within the window defined above
	
Event
	
Date of treatment failure

Death without treatment failure/relapse/other anti-cancer therapy, and
 
 • had SCT, OR • no SCT, and days from the date of last assessment or first dosing date, whichever is later, to the date of death was within the window defined above 	
Event
	
Date of death


No postbaseline assessment, no death
	
Censored
	
Date of first dose

No treatment failure/relapse/death
	
Censored
	
Date of last response assessment (and prior to other anti-cancer therapy if any) or first dosing date, whichever is later

Other anti-cancer therapy started prior to treatment failure/relapse/death	Censored	Date of last response assessment prior to other anti-cancer therapy or first dosing date, whichever is later
Days from last response assessment prior to treatment failure/relapse/death or first dosing date, whichever is later, to treatment failure/relapse/death was not within the window defined above	Censored	Date of last response assessment prior to treatment failure/relapse/death or first dosing date, whichever is later

Censoring Rules for OS:

- For a subject who is not known to have died by the end of study follow-up, OS is censored on the date the subject was last known to be alive.

For EFS or OS in months, the calculation is based on the following formula:

$$(\text{date of event/censoring} - \text{date of first dose} + 1) / 30.4375.$$

EFS and OS will be analyzed using Kaplan-Meier (KM) methods. The KM estimate of the survival function will be computed and the results will be presented using KM curves. The median will be provided along with the corresponding 95% CI. Additionally, the 25% and 75% percentiles for these endpoints will also be provided.

Follow up time for OS will be summarized as continuous variable with descriptive statistics.

- For a subject who is not known to have died by the end of study follow-up, duration of OS follow up in months = $(\text{date of last known to be alive} - \text{date of first dose} + 1) / 30.4375$
- For the remaining subjects, duration of OS follow up in months = $(\text{date of follow-up cutoff} - \text{date of first dose} + 1) / 30.4375$

Data listing for EFS and OS will be presented.

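### SAP Table 6-1 ranks relapse above treatment failure, so a pre-transplant non-responder who remits only after transplant and then relapses gets the later relapse date, contrary to the first-event definition of EFS (minor)

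*SAP*

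**What the plan says.** SAP 6.2.1 measures EFS from the start of study therapy "until the date of treatment failure, AML relapse or death from any cause, whichever occurs first". Protocol 2.2 and 8.1.2 give the same definition.

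SAP 6.2.2 makes a subject a treatment failure if there is at least one efficacy assessment before SCT and other anticancer therapy and "none of these efficacy assessments is CRc, CR, CRi, or PR". It adds that the "date of treatment failure will be the date of last adequate efficacy assessment prior to SCT and other anticancer therapy". For a transplanted subject the failure date is therefore always before the transplant, and responses reached after SCT do not count.

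Table 6-1 then assigns events and censoring, and SAP 6.2.2 says that "the criteria are hierarchical: subjects who meet the criteria on the top will be excluded from the criteria on the bottom". The event rows, in order, are:

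- **Row 1, relapse.** It opens "Relapse, no other anti-cancer therapy or prior to the start of other anti-cancer therapy, and", and its first branch is "had SCT prior to relapse, OR". The time window applies only to the branch without SCT. SAP 6.2.2 also states that "other anti-cancer therapy excludes SCT and conditioning regimen in this table".
- **Row 2, treatment failure.** "Treatment failure, and days from last response assessment prior to treatment failure or first dosing date, whichever is later, to treatment failure" must fall within the group's window.
- **Row 3, death.** It is open only to subjects without treatment failure, relapse or other anti-cancer therapy.

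**The concern.** The definition asks for the earliest of three dates, while the table asks which row comes first. The two agree unless a subject meets both row 1 and row 2 with the failure first. Row 1 requires neither a prior response nor the absence of treatment failure, and SCT and conditioning do not block it. A failure fixed before transplant can therefore be overwritten by a relapse after it.

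The resulting order is wrong. Among otherwise identical pre-SCT non-responders, the one who relapses after transplant is given a longer EFS than the one who stays in remission or who dies without relapse. Time gained after transplant is credited to a subject who had already failed study therapy, and only if that subject relapses. The death row carries an exclusion for prior treatment failure and the relapse row has no matching clause, so this looks like a drafting gap rather than a choice.

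**Working it through.** The plan gives no EFS figure to reproduce, so the check is of the rule. As a first step, the table's windows agree with its own cycle arithmetic: 2 × 28 + 4 = 60, 4 × 28 + 8 = 120 and 8 × 28 + 16 = 240 days.

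**Inputs.** The row order, row conditions and failure definition come from SAP 6.2.2. EFS in months is (event or censoring date − first dose date + 1) / 30.4375, which equals study day / 30.4375. The upper end of the range uses the 3-year limit on follow-up in Protocol 6.5. All subject dates below are assumptions, because the documents contain none.

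**Group A example.** Marrows on days 28 and 56 show no response, and SCT is on day 90. The failure date is day 56. Row 2's window is met: 56 − 28 = 28 days, against a limit of 60.

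| Course after SCT | Row met | Event day | EFS (months) |
|---|---|---|---|
| Alive, no relapse | 2 | 56 | 56/30.4375 = 1.84 |
| Death without relapse, day 100, 180 or 365 | 2 (row 3 closed by the failure) | 56 | 1.84 |
| Other therapy day 150, relapse day 365 | 2 (row 1 fails) | 56 | 1.84 |
| Relapse day 120 | 1 | 120 | 3.94 |
| Relapse day 180 | 1 | 180 | 5.91 |
| Relapse day 365 | 1 | 365 | 11.99 |
| Relapse day 730 | 1 | 730 | 23.98 |
| Relapse day 1095 | 1 | 1095 | 35.98 |

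Under the SAP 6.2.1 definition every line would be 1.84 months. The excess for the relapsing subject runs from 3.94 − 1.84 = 2.1 to 35.98 − 1.84 = 34.1 months.

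**Group B Phase 2 randomized example.** A 5-day lead-in and two 28-day cycles put the Cycle 2 Day 28 marrow on day 5 + 56 = 61. It lies 60 days after first dose, within the 120-day limit. EFS is 61/30.4375 = 2.00 months without relapse or with death, against the same 3.94 to 35.98 months with relapse.

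**Failure outside the window.** Take a Group A subject with a single marrow on day 80, which is 79 days after first dose and beyond 60. Row 2 is not met. Without relapse, or with death, the subject falls to the last row and is censored at first dose (1/30.4375 = 0.03 months). With relapse on day 365 after SCT, row 1 still gives an event at 11.99 months. This case matters for the choice of fix.

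**The case against.** The strongest reply is that the two rows hardly overlap in practice, and most of that reply stands.

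- **Relapse implies remission.** Protocol Appendix 5 describes relapse as disease coming back, so a subject with persistent blasts has nothing to relapse from. The path needs a remission first reached after SCT. This narrows the path without closing it: the failure definition ignores post-SCT responses, and row 1 does not ask when remission was reached.
- **SCT mostly follows response.** Protocol 3.1.2 and 3.4 send Group A subjects to SCT on CR/CRi, and the synopsis does the same for Group B Phase 1b. Only the Group B maintenance text (Protocol 3.1.3 and 3.1.4) leaves SCT open without naming CR/CRi.
- **Late relapses may not be recorded.** Long-term follow-up (Protocol 6.5) lists leukemia treatments, other malignancies and survival, but not relapse. Row 1's SCT branch nevertheless shows that relapses after transplant were anticipated.
- **Little depends on EFS.** It is a secondary endpoint, summarized descriptively with Kaplan-Meier methods, with by-subject listings, in a study that SAP section 1 says is ending early. No decision rule uses it.

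A reader might also infer that MLFS supplies a steady stream of such subjects, since it is not among the responses that prevent failure. Appendix 5 does not support that. MLFS with either count low already meets CRi, and MLFS with both counts recovered and no transfusion dependence meets CR. Only transfusion dependence with recovered counts, or missing counts, leaves MLFS alone.

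**Conclusion.** The inconsistency is real but narrow. Table 6-1 contradicts the EFS definition for a subject who meets all of these conditions: no CRc, CR, CRi or PR before SCT, remission first reached after SCT, and a relapse recorded before any other anti-cancer therapy. For that subject EFS is 3.9 to 36.0 months under the assumed dates, where the definition gives 1.8. The contrast with the subject who does not relapse, or who dies without relapse, holds when the failure is inside row 2's window. A subject who relapses and then dies keeps the relapse date.

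A reader might infer that the reported EFS curves are materially too high, for instance by one subject's weight in Group A for each such case. The documents do not support this. They give no count of such subjects, the count is probably very small, and Group A is where SCT is most clearly tied to CR/CRi. No effect on the Kaplan-Meier estimate is claimed. Severity is minor.

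**What to change.** In Table 6-1, date the EFS event at the earliest of treatment failure, relapse or death that qualifies as an event under its own row's conditions. A qualifying failure before SCT then takes precedence over a later relapse. Limit the hierarchy sentence to the choice between event rows and censoring rows.

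Two apparently simpler edits are not equivalent:

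- Adding a no-failure-before-SCT condition to the relapse row would, in the day-80 example, leave no event row open. A subject with an observed relapse would be censored at first dose. Under the earliest-qualifying rule that relapse stays an event at 11.99 months.
- Simply placing treatment failure above relapse could give a date later than a relapse already recorded in a subject without SCT, because failure is dated at the last adequate assessment.

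The cost is one sentence in SAP 6.2.2 and a small change to the derivation code. EFS becomes shorter for any affected subject and is unchanged for the rest. If the SAP is already final, document the change in the CSR, as SAP section 1 provides.
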